6 TRIAL TREATMENT

6.1 Investigational and Auxiliary Medicinal Products

Trial treatment is defined as any IMP, auxiliary medicinal product (AMP), or medical device(s) intended to be administered to a trial subject according to the trial protocol. IMP(s) specifically are referred to as trial drug(s).

Genmab

Trial treatment should be administered as described in Table 6-1 and Table 6-2 until 1 or more of the discontinuation criteria in Section 7 are met.

Detailed dose modification guidance is provided in Section 6.7. Information regarding concomitant therapy is provided in Section 6.6.

Table 6-1 Investigational Medicinal Product

Trial Drug Name	GEN3017 (DuoBody® CD3xCD30)a,b
Dosage Formulation	Concentrate for solution for CCI injection
Dose (including schedule and cycle length)	CCI
Route of Administration	CCI
Dosing Instructions	In expansion, 1) for adult subjects, GEN3017 will be administered as a injection with CC at the DL determined by the data from the dose escalation part. 2) For adolescent subjects with R/R cHL (US and Australia only; Cohort 2), GEN3017 will be administered as an CC Refer to Section 6.1.2 for premedication and post-GEN3017 treatment requirements. Refer to the IMP Manual for detailed instructions including drug dilution and injection volume.
Hospitalization/ Monitoring Guidance	During dose escalation in treatment Cycle 1, all subjects are required to be hospitalized for 24 hours after each GEN3017 administration. Subjects must be instructed to contact the investigator should signs or symptoms of CRS and/or ICANS occur following discharge from the hospital. During dose expansion in treatment Cycle 1, all subjects are required to remain at the clinic for monitoring CCI of GEN3017 for a minimum of 4 hours and hospitalization for 24 hours for CRS monitoring is required after CCI. Additional and prolonged hospitalization for monitoring subject's safety during GEN3017 administration CCI may be implemented per investigator's discretion. As data accumulate, increased (or reduced) monitoring may be implemented for additional dose administrations if recommended by the sponsor's Safety Committee.
Packaging	GEN3017 will be provided in 2R Glass Vials

Confidential Page 66 of 162

Document Name: GCT3017-01 - Protocol - 18 Oct 2023 Genmab

Document Number: TMF-380962

Version: 3.0

Labeling	Trial drug labels will contain information to meet the applicable regulatory requirements. For further details see the IMP Manual
----------	---

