6.6.3.1 Permitted Concomitant Therapies

The following concomitant medication and therapies are permitted during the trial:

1. SARS-CoV-2 vaccine is generally permitted, including mRNA-based, protein-based, or nonreplicating viral vector-based vaccines. Consider choosing an appropriate type of SARS-CoV-2 vaccine and consult with an infectious disease expert if desired. SARS-CoV-2 vaccine should not be administered during the screening period and DLT observation period.

Confidential Page 72 of 162

Document Number: TMF-380962

Version: 3.0

For other immunizations, physicians should review the subject's vaccination status and subjects should, if possible, be brought up to date with all immunizations in agreement with current immunization guidelines prior to initiating treatment.

Genmab

- 2. Hematopoietic growth factors such as erythropoietin, granulocyte colony-stimulating factor (G-CSF) (filgrastim, pegfilgrastim), granulocyte/macrophage colony-stimulating factor (sargramostim), or thrombopoietin (oprelvekin, eltrombopag) are permitted if clinically indicated. In the case of ≥ grade 3 neutropenia, use of growth factors is mandated in dose escalation and at the investigator's discretion in expansion.
- 3. Red blood cell and platelet transfusions, if clinically indicated.
- 4. Multivitamins, vitamin D, calcium, and supplements for prevention of weight loss.
- 5. Prescribed medicinal cannabinoids as palliative therapy.
- 6. Medications to prevent or treat CRS and ICANS are permitted. Please refer to Section 6.7.2 for AE management guidelines and mitigation plans.
- 7. It is recommended that high-risk subjects (ie, those with a high tumor burden) should be treated prophylactically in accordance with local standards (eg, rehydration, diuretics, allopurinol 300 mg daily, and medication to increase urate excretion). All subjects should be monitored for symptoms of TLS (see Section 10.15). Management of TLS, including dehydration and abnormal laboratory test results such as hyperkalemia, hyperuricemia, and hypocalcemia, is highly recommended.
- 8. Anti-infection prophylaxis for bacterial, viral, fungal, or pneumocystis infections is allowed and should be given per institutional practice.

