		refractory ^a grade 3 for >72 hours or grade 4	Manage CRS per current practice guidelines (Section 10.13) and provide supportive therapy, which may include intensive care.
	ICANS (see Section 10.14)	Grade 1 and grade 2	Withhold GEN3017 until resolution of ICANS event to ≤ grade 1 for at least 72 hours.
			Provide supportive therapy and manage per current practice guidelines.
		Grade 3	Withhold GEN3017 until resolution of ICANS event to ≤ grade 1 for at least 72 hours.
			Provide supportive therapy, which may include intensive care, consider neurology evaluation, and manage per current practice guidelines.
			Recurrent grade 3 ICANS: Permanently discontinue GEN3017.
		Grade 4	Permanently discontinue GEN3017.
			Provide supportive therapy, which may include intensive care, consider neurology evaluation, and manage per current practice guidelines.
Hematological (see Section 6.7.2.1 for details) ^b	Platelet count decreased/	≥ Grade 3	Withhold GEN3017 until platelet count is ≥50 × 10 ⁹ /L.
	thrombocytopenia		Platelet infusions may be administered per institutional standards.
	Neutropenia and febrile neutropenia	≥ Grade 3	Withhold GEN3017 until neutrophil count is $\geq 0.5 \times 10^9 / L$.
			Use of growth factors is mandated.
	Anemia	≥ Grade 3	Withhold GEN3017 until hemoglobin is ≥8 g/dL (≥80 g/L or ≥4.9 mmol/L).
			Red blood cell infusions should be administered per institutional standards.

Confidential Page 78 of 162

Document Number: TMF-380962

Version: 3.0

	Adverse Event(s)	Toxicity Grade or Condition (CTCAE v5.0 Except ASTCT for CRS/ICANS and Cairo- Bishop for TLS/CTLS)	Adverse Event Management	
	TLS/CTLS	Any grade	Withhold GEN3017 until resolution of TLS/CTLS event.	
	Tumor flare reaction	Grade 3 and 4	Withhold GEN3017 until improvement to ≤ grade 1. Monitor for signs and symptoms of compression or obstruction due to mass effect secondary to tumor flare, and institute appropriate treatment (Section 10.15).	
	All other non- hematologic AEs	Grade 3a; first occurrence	Withhold GEN3017 until improvement to ≤ grade 2 or resolution to baseline.	
		Grade 3a; recurrent	Second episode of the same AE considered related to GEN3017:	
Other non-hematologic			Withhold GEN3017 until improvement to ≤ grade 2 or resolution to baseline.	
			Permanently discontinue GEN3017 if no improvement within 14 days unless otherwise agreed upon with the sponsor's medical monitor.	
		Grade 4a; first occurrence	Withhold GEN3017.	
			Initiate proper management of the AE.	

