8.3.8 Other Safety Assessments

8.3.8.1 Neurological Evaluation

Assessment for neurotoxicity with a neurologic assessment must be performed during therapy with GEN3017 by trained trial-site staff. An assessment according to ICANS evaluation (Lee et al., 2019) should be performed as indicated in Section 1.3. ICANS assessments must be performed at least daily during CRS events, and once daily during hospitalization if subject was hospitalized. Finally, additional ICANS assessment should always be performed when clinically indicated.

ICANS is a disorder characterized by a pathologic process involving the CNS following any immune therapy that results in the activation or engagement of endogenous or infused immune effector cells, including T cells. ICANS may occur concurrently with CRS or shortly after CRS symptoms subside (but rarely before). Symptoms can be progressive and may include aphasia, altered level of consciousness, delirium, dizziness, encephalopathy, headache, impairment of cognitive skills, motor weakness, tremor, seizures, and cerebral edema (Lee et al., 2019).

The grading of ICANS requires assessment of the 10-point immune effector cell-associated encephalopathy (ICE) score as well as evaluation of 4 other neurologic domains: level of consciousness, seizures, motor symptoms, and signs of raised intracranial pressure/cerebral edema, which may occur with or without encephalopathy. See Section 10.14 for additional details for grading and management of ICANS.

Overall ICANS grade is determined by the most severe event of the neurotoxicity domains (ICE score, level of consciousness, seizure, motor findings, raised intracranial pressure/cerebral edema) not attributable to any other cause. For example: subject with an ICE score of 3 who has a generalized seizure is classified as having grade 3 ICANS.

A subject with an ICE score of 0 may be classified as having grade 3 ICANS if the subject is awake with global aphasia. But a subject with an ICE score of 0 may be classified as having grade 4 ICANS if the subject is unarousable.

A subject with an abnormal ICE score must be assessed to determine if it is due to ICANS or an alternate cause. If not due to ICANS, the relevant condition will be reported as an AE.

Depressed level of consciousness should not be attributable to another cause (eg, sedating medication).

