10.14 Appendix 14: ASTCT ICANS Consensus Grading and Management

Management Guidelines for Immune Effector Cell-Associated Neurotoxicity Syndrome (ICANS) Based on ASTCT Guidelines

Genmab

Hold GEN3017 until resolution of ICANS.	No concurrent CRS:	
 Supportive care per institutional standard of care Closely monitor neurologic status Recommend initiating prophylactic non-sedating anti-seizure medication until resolution of ICANS Aspiration precautions Recommend brain imaging and EEG per institutional guidelines 	Anticytokine therapy not indicated Concurrent CRS: Anticytokine therapy indicated: Choose alternative to tocilizumab (eg, siltuximab, anakinra) if possible. (Refer to CRS Management Guidance Based on the American Society for Transplantation and Cellular Therapy (ASTCT) Guidelines table in Section 10.13.) Consider anakinra as a daily dose of 100 mg SC or 200 mg SC (100 mg every 12 hours) depending on the severity of neurotoxicity and other concurrent toxicities. Anakinra should be given until resolution of neurotoxicity and other concurrent toxicities which could benefit from anakinra treatment. Consider siltuximab, 11 mg/kg IV over	Dexamethasone, 10 mg IV every 12 hours
 Hold GEN3017 until resolution of ICANS. Supportive care per institutional standard of 	No concurrent CRS: Anticytokine therapy not indicated.	Dexamethasone at 10- 20 mg IV every 12 hours
 Closely monitor neurologic status Recommend initiating prophylactic non-sedating anti-seizure medication until resolution of ICANS (eg, levetiracetam) 	Anticytokine therapy indicated: Choose alternative to tocilizumab (eg, siltuximab, anakinra) if possible. (Refer to CRS Management Guidance	

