 Grade 4 ICE score^a 0 and patient is unarousable or requires vigorous or repetitive tactile stimuli to arouse or stupor or coma Life-threatening prolonged seizure (>5 min); or repetitive clinical or electrical seizures without return to baseline in between Deep focal motor weakness^c such as hemiparesis or paraparesis Diffuse cerebral edema on neuroimaging^d; decerebrate or decorticate posturing; or cranial nerve VI palsy; or papilledema; or Cushing's triad Life-threatening consequences Urgent intervention indicated Requirement for mechanical ventilation 	 Permanently discontinue GEN3017. Management in monitored care or intensive care unit. Supportive care per institutional standard of care Closely monitor neurologic status Recommend initiating prophylactic nonsedating anti-seizure medication until resolution of ICANS (eg, levetiracetam) Aspiration precautions Continuous cardiac telemetry and pulse oximetry as indicated Closely monitor neurologic status with serial neurologic examinations to include fundoscopy. Consider neurology consult. Perform brain imaging (eg, MRI), EEG, and lumbar puncture (with opening pressure) if no contraindications Prophylactic nonsedating anti-seizure medication Levetiracetam/nonsedating anti-seizures Mechanical ventilation may be required Consider imaging of spine for focal motor weakness Lower intracranial pressure (ICP) by hyperventilation, hyperosmolar therapy with mannitol/hypertonic saline, and/or neurosurgery consultation for 	No concurrent CRS: Anticytokine therapy not indicated. Concurrent CRS: Anticytokine therapy indicated: Choose alternative to tocilizumab (eg, siltuximab, anakinra) if possible. (Refer to CRS Management Guidance Based on the American Society for Transplantation and Cellular Therapy (ASTCT) Guidelines table in Section 10.13.) Consider anakinra at a daily dose of 100 mg SC or 200 mg SC (100 mg every 12 hours) depending on the severity of neurotoxicity and other concurrent toxicities. Anakinra should be given until resolution of neurotoxicity and other concurrent toxicities which could benefit from anakinra treatment. Consider siltuximab, 11 mg/kg IV over 1 hour, one time only.	Dexamethasone 10-20 mg IV every 6 hours. If no response, initiate methylprednisolone 1000 mg/day

Genmab

Confidential Page 139 of 162

Version: 3.0

Neurologic Toxicities	Supportive Care	Anticytokine Therapy	Corticosteroids	
	ventriculoperitoneal shunt in patients with cerebral edema			

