ICANS grade is determined by the most severe event (ICE score, level of consciousness, seizure, motor findings, raised ICP/cerebral edema) not attributable to any other cause; eg, a patient with an ICE score of 3 who has a generalized seizure is classified as grade 3 ICANS. Grade 5 is considered to be fatal.

Confidential Page 140 of 162

Version: 3.0

CTCAE=Common Terminology Criteria for Adverse Events; EEG=electroencephalogram; ICE=immune effector cell-associated encephalopathy; ICP=intracranial pressure; N/A=not applicable.

- a. A patient with an ICE score of 0 may be classified as grade 3 ICANS if awake with global aphasia, but a patient with an ICE score of 0 may be classified as grade 4 ICANS if unarousable.
- b. Depressed level of consciousness should be attributable to no other cause (eg, no sedating medication).
- c. Tremors and myoclonus associated with immune effector cell therapies may be graded according to CTCAE v 5.0, but they do not influence ICANS grading.
- d. Intracranial hemorrhage with or without associated edema is not considered a neurotoxicity feature and is excluded from ICANS grading. It may be graded according to CTCAE v 5.0.

Source: (Lee et al., 2019)

The Immune Effector Cell-Associated Encephalopathy (ICE) Assessment Tool

Cognitive Domain	Task	Points	ICE Scoring
Orientation	Orientation to year	1	10: No impairment
	Orientation to month	1	7-9: Grade 1 ICANS
	Orientation to city	1	3-6: Grade 2 ICANS
	Orientation to hospital	1	0-2: Grade 3 ICANS
Naming	Naming 3 common objects (eg, point to clock, pen, button)	3	0 due to subject unarousable and unable to perform ICE assessment: Grade 4 ICANS
Following commands	Ability to follow simple commands, eg, "Show me two fingers" or "Close your eyes and stick out your tongue"	1	
Writing	Ability to write a standard sentence, eg, "Our national bird is the bald eagle"	1	
Attention	Ability to count backwards from 100 by 10	1	
Maximum ICE Sco	re	10	

ICANS= immune effector cell-associated neurotoxicity syndrome; ICE= immune effector cell-associated encephalopathy. Source: (Lee et al., 2019)

Confidential Page 141 of 162

Document Number: TMF-380962

Version: 3.0

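### The protocol gives inconsistent rules for re-dosing GEN3017 after ICANS, and no readable text says which one governs

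*Combined protocol and SAP*

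**What the plan says.** Three places in the protocol govern dosing after ICANS.

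- **Table 6-4 (Section 6.7.2.1), ICANS rows.** For grades 1 and 2, and again for grade 3, the instruction is "Withhold GEN3017 until resolution of ICANS event to ≤ grade 1 for at least 72 hours". Recurrent grade 3 and any grade 4 event end treatment permanently.
- **Appendix 14 (Section 10.14), management table.** The rows below grade 4 say "Hold GEN3017 until resolution of ICANS", with no grade threshold and no waiting time. The grade 4 row says "Permanently discontinue GEN3017".
- **Section 6.7.2.1, general text on DLTs.** A subject with a DLT may continue, with the medical monitor's approval, if the toxicity falls to grade 2 or lower, or to baseline, within 4 weeks. After a grade 4 non-hematologic DLT, resumption may be considered in discussion with the monitor, either on improvement to grade 2 or better or because the subject has benefited. Section 6.7.1 makes grade 4 ICANS a DLT, and also grade 3 ICANS that has not come down to grade 2 or lower within 48 hours of adequate intervention.

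The cross-references run both ways. Section 6.1 says "Detailed dose modification guidance is provided in Section 6.7". Section 6.6.3.1, on medicines for CRS and ICANS, says "Please refer to Section 6.7.2 for AE management guidelines and mitigation plans". Section 8.3.8.1 says "See Section 10.14 for additional details for grading and management of ICANS", and the ICANS row of Table 6-4 itself sends the reader to Section 10.14.

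**The concern.** Grade 1 ICANS is an active event. The ICE tool in Appendix 14 maps the score as "7-9: Grade 1 ICANS", and Section 8.3.8.1 requires attribution before the label is used: "A subject with an abnormal ICE score must be assessed to determine if it is due to ICANS or an alternate cause". A grade 1 event meets the Table 6-4 grade threshold from the moment it starts, so only the 72-hour clock stands between onset and the next dose. Appendix 14 would keep the same subject off drug until the event clears.

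This is a first-in-human trial. Section 2.3.2 names ICANS as a potential main risk and Section 8.4.1.1 lists it as an adverse event of special interest. Section 6.7.2 allows dose delay but not dose reduction, so the hold rule is the main dosing control short of stopping. Two sites relying on different sections could reach opposite decisions for the same subject. Section 6.7.2.2 carries the guidance into expansion as appropriate, so both parts are affected.

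**Working it through.** The protocol gives no figure to reproduce. The check sets the texts side by side and then compares release times.

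**1. The terms are not interchangeable.** Within Table 6-4, grade 1 and 2 CRS and tumor lysis are held to resolution, grade 3 CRS needs symptoms resolved for 72 hours, tumor flare needs improvement to grade 1 or less, and ICANS needs grade 1 or less for 72 hours. The table separates full resolution from a fall to grade 1, so resolution in Appendix 14 cannot safely be read as grade 1 or less.

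**2. Release times for grades 1, 2 and first-episode grade 3.** Let d be the hours from first being at grade 1 or less until ICANS resolves, with no later worsening; for a grade 1 event this is onset to resolution.

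- Table 6-4 releases at 72 h.
- Appendix 14 releases at d h.
- Difference (Appendix 14 minus Table 6-4) = d − 72.
- A rule that meets both releases at max(72, d).

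The documents give no ICANS durations, so d is an assumed range.

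| d (h) | Table 6-4 | Appendix 14 | Difference | Rule meeting both |
|---|---|---|---|---|
| 24 | 72 | 24 | −48 | 72 |
| 72 | 72 | 72 | 0 | 72 |
| 96 | 72 | 96 | +24 | 96 |
| 168 | 72 | 168 | +96 | 168 |
| 240 | 72 | 240 | +168 | 240 |

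The rules agree only at d = 72. Above it, Table 6-4 permits a dose during active grade 1 ICANS and Appendix 14 does not. Below it, Appendix 14 permits a dose after resolution and Table 6-4 does not. The difference matters only if a dose falls due between the two release times.

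**3. ICANS that is a DLT.**

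| Event | General DLT text, 6.7.2.1 | Table 6-4 | Appendix 14 |
|---|---|---|---|
| Grade 3, first episode | May continue at grade 2 or less, or baseline, within 4 weeks, with monitor approval | Grade 1 or less for 72 h | Resolution |
| Grade 4 | Resumption may be considered | Permanent stop | Permanent stop |

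Grade 3 therefore has three release standards, and grade 4 has two incompatible instructions.

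**4. Precedence.** Sections 6.1 and 6.6.3.1 and the pointer to Table 6-4 in Section 6.7.2.1 lead to Section 6.7. Sections 6.1.2 and 8.3.8.1 and the ICANS row of Table 6-4 lead to Section 10.14. Each says where guidance is found; none says which text prevails. Appendix 15 refers to Table 6-4 for tumor flare dose modification; Appendix 14 has no such sentence in its readable text.

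**The case against.** The strongest reply is that the protocol already divides the subject: Section 6.7 covers dosing decisions, and Appendix 14 supplies clinical management. Section 6.7.2 introduces dose delay as described in what follows it, and Section 8.3.8.1 calls Appendix 14 additional detail. On that view an investigator deciding on a hold uses Table 6-4. Similarly, the table's row for all other non-hematologic grade 4 events repeats the general resumption conditions, which suggests those were meant for events without their own row. This is a reasonable account of intent and makes divergent practice less likely. It does not settle the point: Appendix 14 carries its own hold instruction, and the general DLT text has no exception for ICANS.

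Several mitigations stand. A site that meets the strictest condition breaches no text. Monitor approval is needed to continue after a DLT, and to resume after a non-DLT toxicity delay of more than 4 weeks from the last dose. Grade 1 and 2 ICANS are not listed DLTs, however, so the DLT approval does not reach them. Section 8.4.3.5 requires reporting to the sponsor within 24 hours if serious and 72 hours if not, which is oversight rather than approval to re-dose. Section 2.3.2 reports no ICANS in cHL patients in the cited CAR-T trials and expects low grade and frequency in cHL; it gives no such expectation for TCL.

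A reader might infer that re-dosing at stable grade 1 is unsafe, or that it will happen often. The documents support neither. Tolerating residual grade 1 is a clinical judgment, and frequency cannot be estimated.

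**Conclusion.** The inconsistency is real and should be corrected. For grades 1, 2 and first-episode grade 3, Table 6-4 and Appendix 14 release the hold at different times unless ICANS spends exactly 72 hours at grade 1 or less before resolving. Over the assumed 24 to 240 hours, the gap runs from Appendix 14 being 48 hours earlier to 168 hours later. The later case is the one that bears on safety.

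A reader might infer that the mismatch arises only when grade 1 ICANS outlasts 72 hours, or that grade 4 is free of it because Table 6-4 and Appendix 14 agree there. Neither inference holds: early resolution reverses the difference, and the general DLT text leaves resumption open after grade 4.

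The conclusion rests on two assumptions. The first two Appendix 14 rows, whose grade labels are not legible, are taken as grades 1 and 2 because two rows with the hold instruction precede the labeled grade 3 row. No redacted text is taken to set precedence. With durations absent and the dosing interval redacted, practical frequency is unknown and may be low.

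**What to change.** 1. In the ICANS rows of Table 6-4, state one rule that satisfies both current texts. For grades 1, 2 and first-episode grade 3, require resolution of ICANS and at least 72 hours at grade 1 or less before the next dose. Keep permanent discontinuation for recurrent grade 3 and for grade 4.
2. In Appendix 14, repeat that rule or defer to Table 6-4, as Appendix 15 does for tumor flare.
3. In the general DLT text of Section 6.7.2.1, add that the ICANS rows of Table 6-4 override the resumption conditions given there.

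The change is to protocol wording only. Its cost is a possibly longer hold: d − 72 extra hours against Table 6-4 when d exceeds 72, and 72 − d extra hours against Appendix 14 when d is shorter. In Cycle 1 a long hold could cost DLT evaluability. Section 6.7.1 allows delays only if shorter than one cycle, Section 9.2 requires a subject without a DLT to complete the observation period, and Section 4.1.1.5 replaces subjects who are not evaluable.

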6.7 Dose Modification and Stopping Rules

6.7.1 Dose-Limiting Toxicity (Dose Escalation of GEN3017)

Treatment delays during the first CCI of the start of the DLT window are allowed if they are less than 1 cycle in length; under these circumstances, the DLT window can be extended up to CCI.

All DLTs are required to be reported to the sponsor within 24 hours of occurrence.

Confidential Page 74 of 162

Document Number: TMF-380962

Version: 3.0

All AEs including DLTs will be graded for severity according to the National Cancer Institute (NCI)-CTCAE, v5.0 unless otherwise specified. CRS and ICANS will be evaluated according to the ASTCT criteria (Lee et al., 2019). Clinical tumor lysis syndrome (CTLS) will be evaluated according to the Cairo-Bishop classification ((Coiffier et al., 2008); Section 10.15).

Genmab

The occurrence of any of the toxicities outlined in this section will be considered as a DLT except those that are clearly due to the underlying disease or extraneous cause:

- All grade 5 toxicities
- Hematological toxicities listed below:
 - o Grade 4 neutropenia (ie, absolute neutrophil count $<0.5\times10^9$ cells/L [$<500/\mu$ L]) lasting >7 days not attributable to underlying disease
 - o Grade 3 and grade 4 febrile neutropenia (neutrophil count <1.0×10⁹ cells/L with a single temperature of >38.3 °C [100.9 °F] or with a sustained temperature of ≥38 °C [≥100.4 °F] for more than 1 hour) lasting >2 days
 - Grade 4 thrombocytopenia (platelet count ≤25.0×10⁹ platelets/L [<25,000/μL]) for >7 consecutive days not attributable to underlying disease, or ≥ grade 3 thrombocytopenia (<50.0×10⁹ platelets/L) of any duration with clinically significant bleeding or ≥ grade 3 thrombocytopenia requiring a platelet transfusion
 - Grade 4 anemia
- Non-hematological toxicities listed below:
 - o Grade 4 CRS according to ASTCT criteria (Lee et al., 2019)
 - o Grade 3 CRS according to ASTCT criteria (Lee et al., 2019) which has not resolved to ≤ grade 2 within 48 hours following adequate intervention
 - o Grade 4 ICANS according to ASTCT criteria (Lee et al., 2019)
 - o Grade 3 ICANS according to ASTCT criteria (Lee et al., 2019) which has not resolved to ≤ grade 2 within 48 hours following adequate intervention
 - o TLS grade 3 that has not resolved within 5 days
 - o TLS grade 4
 - Any ≥ grade 3 (severe or life-threatening) non-hematological toxicities, excluding the following:

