 - a. If platelet count is $<50 \times 10^9/L$, hold dose until platelet count is $\ge 50 \times 10^9/L$.
 - b. If febrile neutropenia is $<0.5 \times 10^9$ /L, hold dose until neutrophil count is $\ge 0.5 \times 10^9$ /L.
 - c. If hemoglobin is <8 g/dL (<80 g/L or <4.9 mmol/L), hold dose until hemoglobin is ≥8 g/dL (≥80 g/L or ≥4.9 mmol/L).

Note: If the investigator deems any of the above cytopenia as bone marrow involvement due to the disease, continuation of GEN3017 treatment can be discussed with the sponsor's MM. Transfusion with blood products and/or administration with G-CSF is permitted if clinically indicated.

If a dose delay occurs, then PK and biomarker assessments should be performed on or relative to the actual day of trial drug administration, not on the original scheduled administration day.

Refer to Table 6-4 for dose modification guidelines for specific AEs (including guidance for permanent discontinuation of treatment).

Table 6-4 Dose Modification Guidelines for Specific Adverse Events

	Adverse Event(s)	Toxicity Grade or Condition (CTCAE v5.0 Except ASTCT for CRS/ICANS and Cairo- Bishop for TLS/CTLS)	Adverse Event Management	
Immune system disorder		Grade 1 and grade 2	Withhold GEN3017 until resolution of CRS event. Provide supportive therapy and manage per current practice guidelines.	

Confidential Page 77 of 162

Version: 3.0

	Adverse Event(s)	Toxicity Grade or Condition (CTCAE v5.0 Except ASTCT for CRS/ICANS and Cairo- Bishop for TLS/CTLS)	Adverse Event Management
			If grade 2 CRS occurs with CC or beyond, administer CRS prophylaxis with the next dose until an GEN3017 dose is given without subsequent CRS (of any grade).
		Grade 3	Withhold GEN3017 until resolution of CRS event.
	CRS (see Section 10.12 and Section 10.13. If CRS is refractory to management, consider other causes		Ensure CRS symptoms are resolved for at least 72 hours prior to the next dose of GEN3017.
			If grade 3 CRS occurs or beyond, administer CRS prophylaxis with the next dose until a GEN3017 dose is given without subsequent CRS (of any grade).
	including		Hospitalize for the next dose of GEN3017.
	macrophage activation syndrome		Recurrent grade 3 CRS:
	and hemophagocytic		Permanently discontinue GEN3017.
	lymphohistiocytosis)		Manage CRS per current practice guidelines (Section 10.13) and provide supportive therapy, which may include intensive care.
		Cytokine blockade-	Permanently discontinue GEN3017.

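### The Table 6-4 neutrophil hold has no effect at grade 3, and Table 6-4 and Section 6.7.2.1 disagree on what triggers it and how binding it is

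*Combined protocol and SAP*

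**What the plan says.** Four places in the protocol bear on dosing during neutropenia.

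- **Table 6-4, hematological block.** The row is labelled "Neutropenia and febrile neutropenia" and its grade column is grade 3 or higher. The action is "Withhold GEN3017 until neutrophil count is" at least 0.5 × 10⁹/L, and growth factors are mandatory. The block refers to Section 6.7.2.1 for details.
- **Section 6.7.2.1, laboratory rule b.** "If febrile neutropenia is $<0.5 \times 10^9$ /L, hold dose until neutrophil count is" at least 0.5 × 10⁹/L. The sentence introducing rules a to c says that the dose can be held, which is permissive.
- **Section 6.7.1, DLT criteria.** These supply the count boundaries: "Grade 4 neutropenia (ie, absolute neutrophil count" below 0.5 × 10⁹/L), and "Grade 3 and grade 4 febrile neutropenia (neutrophil count <1.0×10⁹ cells/L" with fever). Grade 4 neutropenia is a DLT if it lasts more than 7 days, and febrile neutropenia if it lasts more than 2 days.
- **Section 6.7.2.1, first bullet.** After a DLT, treatment is interrupted. It may continue if the toxicity recovers to grade 2 or better, or to baseline, within 4 weeks, with medical monitor approval.

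Section 6.7.2.2 carries this guidance into the expansion cohorts as appropriate.

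**The concern.** A hold rule needs a trigger and a release that do not overlap; otherwise an event can start and end the hold at the same moment. In the neutrophil row the release count is the boundary between grades 3 and 4, while the trigger is set one grade lower. A site that turns to Section 6.7.2.1 for clarification finds a rule that applies to a different set of subjects and is worded as optional.

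Section 8.3.7 requires hematology to be reviewed before each administration so that the subject can be dosed according to the protocol's instructions, so the question can arise at every dose. Sites working from the table, from rule b or from the DLT bullet could reach different dosing decisions on the same blood count. Dose delays and exposure, which feed the overall judgement on the recommended phase 2 dose, could then partly reflect how a site reads the text.

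**Working it through.** The plan states no figure to reproduce here, so the check is one of logic.

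**Inputs** (counts *x* in 10⁹/L)

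- Grade 4 neutropenia: *x* < 0.5 (Section 6.7.1). Grade 3 therefore starts at *x* = 0.5.
- Febrile neutropenia, grades 3 and 4: *x* < 1.0 plus fever (Section 6.7.1).
- Table 6-4: trigger is grade 3 or higher; release is *x* ≥ 0.5.
- Rule b: trigger is febrile neutropenia with *x* < 0.5; release is *x* ≥ 0.5.
- Upper limit *U* of afebrile grade 3: not printed. Assumed to be 0.75 or 1.0.

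**Rule.** A hold is in force when its trigger is met and its release is not.

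- Table 6-4, afebrile: (*x* < *U*) and (*x* < 0.5) reduces to *x* < 0.5 for any *U* above 0.5.
- Table 6-4, febrile: (*x* < 1.0) and (*x* < 0.5) reduces to *x* < 0.5.
- Rule b: in force only if febrile and *x* < 0.5.

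| Count | Fever | Table 6-4 triggered | Release met | Table 6-4 hold in force | Rule b hold |
|---|---|---|---|---|---|
| 0.4 | no | yes | no | **yes** | **no** |
| 0.4 | yes | yes | no | yes | yes |
| 0.5 | no | yes | yes | no | no |
| 0.6 | no | yes | yes | no | no |
| 0.6 | yes | yes | yes | no | no |
| 0.9 | no | only if *U* = 1.0 | yes | no | no |
| 0.9 | yes | yes | yes | no | no |

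**Width of the void band** (triggered, but released at once)

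- Febrile neutropenia: 1.0 − 0.5 = 0.5.
- Afebrile grade 3: *U* − 0.5, which is 0.75 − 0.5 = 0.25 or 1.0 − 0.5 = 0.5.

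The choice of *U* changes the width of the band but not the conclusion. Because Section 6.7.1 gives both grades of febrile neutropenia the same count criterion, a grade 4 febrile event with a count of 0.5 or more is also released at once.

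**Comparison with the neighbouring rules.** Section 6.7.1 prints grade 3 or higher thrombocytopenia as below 50 × 10⁹/L, and Table 6-4 releases at 50 or above: overlap 50 − 50 = 0. Hemoglobin rule c triggers below 8 g/dL and releases at 8 or above: overlap 8 − 8 = 0.

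**Table against rule b.** The two differ in effect in the first line of the table above: an afebrile count below 0.5 is held by Table 6-4 but not by rule b read literally. They differ in nominal trigger over the whole void band. They also differ in force, one being an instruction and the other a permission.

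**DLT overlap.** Take a subject with grade 4 neutropenia for more than 7 days whose count recovers to 0.5. The Table 6-4 release is met. The DLT bullet is not, because 0.5 is grade 3, unless that was the subject's baseline. Table 6-4 makes no exception for DLTs, so this subject has two release criteria.

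**The case against.** The strongest reply is that the rule is clear enough once the two parts are read together. The table sends the reader to Section 6.7.2.1, where the numbers in rule b meet at 0.5 exactly as those for platelets meet at 50 and hemoglobin at 8. The hemoglobin row of the table also prints only a grade, and rule c supplies its count. On this reading the grade column of the neutrophil row serves the growth-factor instruction, which does act at grade 3 and matches the threshold in Section 6.6.3.1 for dose escalation, while the count governs the hold. Dosing at grade 3 may even be intended: footnote b of Table 6-4 sets no limit on manageable hematological toxicities in subjects who benefit. The DLT rules also interrupt treatment for the qualifying prolonged events.

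Much of this stands. The row is not idle at grade 3, and dosing at grade 3 is not clearly against the plan. But if the intent is a hold below 0.5, the table's grade and rule b's restriction to febrile cases both misstate it, and the difference between instruction and permission remains. The DLT bullet adds a further criterion instead of settling the matter.

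Three stronger readings are tempting and are not supported:

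- A reader might infer that the hold cannot operate at all. It does: a count below 0.5 triggers it and is held until recovery.
- A reader might infer that no release level is defined. The same 0.5 is printed in both the table and rule b; it simply has no effect at grade 3.
- A reader might infer that reported neutropenia rates will be distorted. The documents do not show this. They give no expected rate of grade 3 neutropenia, and Section 9.3.4 assigns laboratory grades by program from observed values.

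**Conclusion.** The point holds as an internal inconsistency of limited reach. As written, the Table 6-4 hold for grade 3 or higher works as a hold for counts below 0.5 × 10⁹/L. It has zero duration for grade 3 neutropenia and for febrile neutropenia from 0.5 to below 1.0. Rule b names a narrower, permissive trigger, and for DLTs a different recovery criterion applies. No other section settles which prevails.

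This rests only on the grade 4 boundary printed in Section 6.7.1 and the release printed in Table 6-4. The assumed upper limit of grade 3 affects only the width of the void band. How many subjects would fall in that band cannot be estimated from the documents. No sample size, error rate or endpoint definition is affected, so the point is minor, but it concerns a dosing-safety rule and is worth correcting.

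**What to change.** Reconcile the following across Section 6.7.1, Section 6.7.2.1 (the DLT bullet and rule b) and Table 6-4:

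1. The trigger: make the grade or count that starts the hold the same in the table and in rule b.
2. The release: state a count that is consistent with the trigger.
3. The scope of rule b: say whether it covers all neutropenia or only febrile neutropenia, and express its trigger as a count plus, if meant, fever.
4. The force: say whether the hold is mandatory or optional, in the same terms in both places.
5. The DLT case: say which recovery criterion applies when the neutropenia is also a DLT.

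Which threshold is clinically right is for the sponsor to decide; none is proposed here. The cost is protocol wording only, with no change to the design or the analyses. The summary of changes records a similar correction to the hemoglobin values in Section 6.7.2.1 and Table 6-4, made as an administrative update.
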